5.4.7. Dose Reductions

Following dosing interruption or cycle delay due to toxicity, the PF-06952229 dose may need to be reduced when treatment is resumed.

Dose reduction/discontinuation of PF-06952229 should be considered before or concurrently with enzalutamide (for patients receiving combination of PF-06952229 and enzalutamide).

No specific dose adjustments are recommended for Grade 1/2 treatment-related toxicity. However, investigators should always manage their patients according to their medical judgment based on the particular clinical circumstances.

Patients experiencing recurrent and intolerable Grade 2 toxicity may resume dosing at the next lower dose level once recovery to Grade ≤1 or baseline is achieved within 2 weeks.

Dose reduction of PF-06952229 associated with treatment related toxicity by 1 and, if needed, 2 dose levels will be allowed depending on the type and severity of toxicity encountered. Patients requiring more than 2 dose reductions will be discontinued from the treatment and entered into the follow-up phase, unless otherwise agreed between the investigator and the sponsor. All dose modifications/adjustments must be clearly documented in the patient's source notes and case report form (CRF).

Once a dose has been reduced for a given patient, all subsequent cycles should be administered at that dose level, unless further dose reduction is required. Intrapatient dose re-escalation is not allowed.

Patients experiencing a DLT during the 28 day safety window and who in the judgment of the investigator and sponsor are benefiting from therapy may resume dosing at the next lower dose level once adequate recovery is achieved.

Hold PF-06952229 for related Grade 3 AEs with subsequent dose-reduction, if such AEs return to Grade <1 or baseline within two weeks.

Exclusions to this include emesis, and clinically insignificant laboratory abnormalities that resolved within two days on optimum treatment and dose reduction may not be required.

Patients who require a treatment interruption >4 weeks should discontinue the study drug thought to be responsible for the treatment interruption.

Table 3. Dose Modifications for PF-06952229 - Related Toxicity

Toxicity	Grade 1	Grade 2	Grade 3	Grade 4
Serum bilirubin (Guidance for non-Gilbert's Syndrome patients. Agreement between sponsor and investigator is required for these patients).	Continue at the same dose level	Continue at the same dose level	When serum bilirubin ≥2 x ULN: Hold administration until recovery to Grade 0-1 within 2 weeks, serum bilirubin <2 xULN or baseline and reduce by 1 dose level. Discontinue dose if dose delay is more than 2 weeks.* If toxicity reoccurs despite reduction, patient may be dose reduced again by another dose level upon recovery to Grade 0-1 or baseline within 2 weeks unless the patient is in the first dose group, then only 1 dose reduction is allowed. Prompt palliative measures are strongly encouraged (eg, anti-emetics).	Patients who experience related Grade 4 non- hematologic toxicities despite optimal medical intervention should be discontinued from the study. *
Thrombocytopenia	Continue at the same dose level.	Continue at the same dose level.	Hold PF-06952229 until platelets ≥75,000/mm3. For platelet counts 10,000 – 25,000/mm³, continue monitoring every 3 days until recovery to ≥25,000/mm3 (Grade 3 or less) within 2 weeks. For platelet counts ≤10,000/mm3 monitor daily until recovery to ≥25,000/mm3 (Grade 3 or less) within 2 weeks. Reduce PF-06952229 by 1 dose level. If toxicity reoccurs despite dose reduction, patient may either be held until recovery within 2 weeks and continuation at same dose, or undergo further dose reduction by another dose	Consider Permanent discontinuation of study drugs for related Grade 4 AEs of any duration.

 Table 3.
 Dose Modifications for PF-06952229 - Related Toxicity

Toxicity	Grade 1	Grade 2	Grade 3	Grade 4
			level unless the patient is in the first dose group, then only 1 dose reduction is allowed.	
Non-hematologic	Continue at the same dose level.	Continue at the same dose level.	Withhold dose until toxicity is Grade ≤1, or has returned to baseline, within 2 weeks then resume treatment at the same dose level or reduce the dose by 1 level at the discretion of the investigator.*	Permanent discontinuation of study drugs for related Grade 4 AEs of any duration. * (Exclusion to this discontinuation for emesis, and clinically insignificant laboratory abnormalities that resolve within two days on optimum treatment, additional exclusions will require agreement between the investigator and sponsor).
Hematologic	Continue at the same dose level.	Continue at the same dose level.	Withhold dose until toxicity is Grade ≤2, or has returned to baseline within 2 weeks, then resume treatment at the same dose level.**	Permanent discontinuation of study drugs for related Grade 4 AEs of any duration.** (Exclusion to this will require agreement between the investigator and sponsor).
Acute reductions in hemoglobin	Mild symptoms; investigate for tumor hemorrhage or other sources of bleeding.	Moderate symptoms. For acute hemoglobin reduction ≥2g/dL, hold dose and investigate for tumor hemorrhage or other sources of bleeding.	For acute unexplained G ≥3 anemia (hemoglobin <8.0 g/dL), restore blood/blood volume and investigate for tumor hemorrhage or other sources of bleeding. Consider permanent discontinuation. Continuation will require agreement with Sponsor, hemoglobin >9.0 g/dL and complete resolution of the tumor hemorrhage/ bleeding event.	For acute unexplained G ≥4 anemia, replace blood/blood volume and investigate for tumor hemorrhage or other sources of bleeding. Permanent discontinuation of study drug.

^{*}Patients may continue on trial if they are receiving clinical benefit after discussion between the investigator and sponsor.

^{**}Cycle will not be extended to cover for the missing doses.

Nausea, vomiting, or diarrhea should follow guidance for the below:

Table 4. Nausea, Vomiting, or Diarrhea, Cardiac Toxicity Dose Modification Guidance

Initial management or low-grade symptoms	Follow-up or higher-grade symptoms
Dyspepsia Consider starting or giving prescription antacids (not PPIs.	For Grade ≥2, consider dose interruption until dyspepsia back to baseline. Can restart at starting dose or dose modify (eg, 1 level) depending on the severity of symptoms and other contributing factors. Consider referral to gastroenterology for evaluation of Helicobacter pylori, possible endoscopy if Grade ≥2 symptoms persist despite appropriate therapy with antacids and dose interruption.
Diarrhea Prescribe loperamide or diphenoxylate/atropine; begin if diarrhea ≤ Grade 1.	Grade 2: interrupt PF-06952229; restart when it is Grade ≤1 at same dose or at dose reduction, depending on severity of symptoms and other contributing factors.
Nausea/emesis Pretreatment with antiemetics is not required for PF-06952229. Patient education regarding this common side effect is essential, and prescriptions for prochlorperazine, 5-HT3 antagonists, or other antiemetics of choice should be given along with instructions and indications for use if nausea/emesis is Grade 1.	Grade 2: interrupt PF-06952229; consider adding a second antiemetic per NCCN guidelines; restart PF-06952229 when it is Grade ≤1 at same dose or at a dose reduction based on the severity of symptoms.
Cardiac Toxicity	No dose adjustments or reductions are allowed, and patients are to discontinue the study treatment at any signs of medically significant cardiac toxicity.

For enzalutamide, if a patient experiences $a \ge Grade 3$ toxicity or an intolerable side effect (at the PI's discretion), withhold dosing for 1 week or until symptoms improve to $\le Grade 2$, then resume at the same or a reduced dose (120 mg or 80 mg). Please contact Sponsor's medical monitor for any questions.

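### For Grade 3 events under the general Hematologic row of Table 3, Protocol 5.4.7 states two different re-treatment doses and recovery grades and does not say which governs

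*Protocol*

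**What the plan says.** The running text of Protocol 5.4.7 states a rule for related Grade 3 adverse events of any type: "Hold PF-06952229 for related Grade 3 AEs with subsequent dose-reduction", provided that the event recovers to below Grade 1 or to baseline within two weeks. It then adds "Exclusions to this include emesis, and clinically insignificant laboratory abnormalities that resolved within two days on optimum treatment". Hematologic toxicity is not named among these exclusions.

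Table 3, in the same section, gives Grade 3 instructions by toxicity type:

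- Hematologic row: "Withhold dose until toxicity is Grade ≤2, or has returned to baseline within 2 weeks, then resume treatment at the same dose level". No reduction option is given, and the footnote to the cell says only that the cycle is not lengthened to make up missed doses.
- Non-hematologic row: hold until Grade 1 or lower or baseline, "then resume treatment at the same dose level or reduce the dose by 1 level at the discretion of the investigator".
- Thrombocytopenia row: "Reduce PF-06952229 by 1 dose level".
- Serum bilirubin row: reduction by one level after recovery.
- Acute hemoglobin row: "Consider permanent discontinuation. Continuation will require agreement with Sponsor". No dose on resumption is stated.

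Protocol 5.4.5 bases the dose on resumption on the dose reduction criteria, unless investigator and sponsor expressly agree otherwise. Protocol 5.4.6 refers the reader to the Dose Reductions section. SAP 6.1 (Treatment Administration/Compliance) says intrapatient dose reductions are not permitted unless, after discussion with the sponsor, a dose level is deemed beyond the MTD.

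**The concern.** A site treating a related, clinically relevant Grade 3 neutropenia finds two answers in one section: restart at a lower dose, or restart at the same dose. The recovery grade that permits restart also differs. This is a re-treatment safety decision, and its effects last. Under 5.4.7 a reduced dose cannot be raised again, and a patient who needs more than two reductions leaves treatment unless otherwise agreed.

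There is also a reporting consequence. SAP 6.1 tabulates, by dose level, the number of patients with dose reductions, the reasons, and the number of cycles before the first reduction. Protocol 3.4 bases the RP2D on safety, tolerability and early signs of efficacy. If sites follow different sentences, the same toxicity yields different reduction counts at the same dose, and the table partly measures which sentence was followed.

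**Working it through.** The plan states no figure to reproduce, so the check compares the 5.4.7 text with each Grade 3 rule. The text says to reduce after recovery.

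| Related Grade 3 event | Specific rule on resumption | Against the 5.4.7 text |
|---|---|---|
| General Hematologic row (eg, neutropenia) | Same dose level | Direct conflict |
| Non-hematologic row | Same dose or one level lower, investigator decides | Partial conflict |
| Thrombocytopenia row | One level lower | Agrees |
| Serum bilirubin row | One level lower | Agrees |
| Acute hemoglobin row | No dose stated; sponsor agreement needed | Separate rule |
| Bleeding (5.4.8) | Patient discontinued | Separate rule |
| Medically significant cardiac toxicity (5.4.4, Table 4) | Treatment discontinued | Separate rule |
| DLT in a patient who is benefiting (5.4.7) | Next lower level | Own sentence, same direction |

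**Recovery grade.** The text requires below Grade 1 or baseline. The Hematologic row requires Grade 2 or lower or baseline. Take a patient with a normal baseline whose event improves to Grade 2 within two weeks. The table permits restart at the same dose, but the text's condition is not met. The Non-hematologic row uses Grade 1 or lower. Protocol 5.4.6 adds restart conditions of its own: ANC at least 1,000/mm³, and platelets at least 50,000/mm³ where the Thrombocytopenia row of Table 3 says 75,000/mm³.

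**Precedence.** 5.4.6 points to the section that contains both rules. 5.4.5 points to the dose reduction criteria without saying whether these are the text or the table. The SAP 6.1 sentence fits neither, since both the text and several table rows provide for reductions because of toxicity.

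**How many events.** Appendix 10 (Part 1A, 19 June 2020) reports 25 Grade 3 events: 3 attributed to the drug, 21 considered unrelated and 1 (fatigue) with no relationship reported (3 + 21 + 1 = 25). The 3 attributed events are one anemia and two hemorrhages. The hemorrhages fall under the bleeding rule in 5.4.8, so 3 − 2 = 1 candidate remains among 20 patients (1/20 = 5%). That anemia may itself belong to the acute hemoglobin row. Protocol 1.5 notes, however, that low platelet, neutrophil, lymphocyte or white-cell counts were the most common related events of Grade 3 or higher in studies of another inhibitor of this target in advanced solid tumors and glioblastoma.

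**Effect on a reported rate.** One patient handled under the other rule changes the proportion with a reduction by 1/n. For the 6 to 12 patients expected at the MTD (Protocol 9.6.1), this is 1/6 = 16.7 to 1/12 = 8.3 percentage points. In Part 2A it is 1/10 = 10 points, and in Part 2B 1/20 = 5 points.

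**The case against.** The strongest reply is that the specific row overrides the general sentence. 5.4.7 opens by saying the dose may need to be reduced and ties reduction to the type and severity of the toxicity, and Table 3 is organised in just that way. Investigator and sponsor can also agree another course under 5.4.5. This is a reasonable reading, but the protocol does not state it, and a case-by-case agreement does not settle the default.

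A reader might infer that text and table disagree for every related Grade 3 event, or for all hematologic toxicity. The documents do not support that. Thrombocytopenia and bilirubin are reduced under both. Acute hemoglobin reductions, bleeding, cardiac toxicity and DLTs have their own rules. A one-level reduction under the Non-hematologic row satisfies both text and table. Nor can one say that emesis and minor laboratory changes are the only exceptions, because the text says that exclusions include these and does not close the list.

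The recovery threshold below Grade 1 in the text may be a slip for Grade 1 or lower, which is used nearby for Grade 2 events and in the Non-hematologic row. If so, the non-hematologic thresholds agree, but the Hematologic row at Grade 2 or lower still differs.

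Finally, MTD decisions rest on first-cycle DLTs, and dose reductions are only summarised descriptively. That stands and limits the consequence.

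**Conclusion.** The conflict is real but narrow. For related Grade 3 events under the general Hematologic row, 5.4.7 gives two re-treatment doses and two recovery grades, with no order of precedence. This excludes thrombocytopenia, acute hemoglobin reductions, DLTs, and clinically insignificant laboratory changes that clear within two days. The discretionary wording for non-hematologic events and the SAP 6.1 restriction are secondary inconsistencies on the same question.

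The expected number of affected patients is small on the data shown, at most 1 of 20. That count assumes the preliminary Part 1A data in Appendix 10 are a fair guide to later cohorts and to the combination with enzalutamide, which they may not be. The point bears on consistent patient handling and on the dose-reduction tables. It does not bear on the sample size or the mTPI decision rules.

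**What to change.** The sponsor should reconcile the 5.4.7 text with the Hematologic and Non-hematologic rows of Table 3 on two items: the dose after a related Grade 3 event, and the recovery grade required before restart. The protocol should state whether text or table governs when they differ. The restart conditions in 5.4.6, including the platelet threshold, should be aligned in the same edit, and the SAP 6.1 sentence on intrapatient reductions should be made to match. Which rule applies is the sponsor's clinical decision; none is proposed here.

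The cost is a few lines of wording in a protocol amendment and one sentence in the SAP. No endpoint, sample size or analysis method changes. If patients have already been re-treated under the present wording, a short listing of related Grade 3 hematologic events with the dose before the hold and on resumption would show which instruction was followed.

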5.4.6. Dose Delays

Re-treatment following treatment interruption for PF-06952229 treatment-related toxicity or at the start of any new cycle may not occur until all of the following parameters have been met:

- ANC $\ge 1,000 / \text{mm}^3$;
- Platelets count $\geq 50,000/\text{mm}^3$;
- Non-hematologic toxicities have returned to baseline or Grade ≤1 severity (or at the investigator's discretion, Grade ≤2 if not considered a safety risk for the patient).

If a treatment delay results from worsening of hematologic or biochemical parameters, the frequency of relevant blood tests should be increased as clinically indicated.

If these conditions are met within 4 weeks of treatment interruption, PF-06952229 may be resumed. Refer to the Dose Reductions section for AEs that require dose reduction at the time of treatment resumption.

If these conditions are not met, treatment resumption must be delayed for up to a maximum of an additional 2 weeks. If patients require discontinuation of PF-06952229 for more than 6 weeks at any time during the study, then study treatment should be permanently discontinued unless the investigator's benefit/risk assessment suggests otherwise after discussion with the sponsor's medical monitor or designee.

If a treatment interruption continues beyond Day 14 of the current cycle, then the day when treatment is restarted will be counted as Day 1 of the next cycle.

If patients require discontinuation of study drug for more than 4 weeks at any time during the study, then study treatment should be permanently discontinued, unless the investigator's benefit/risk assessment suggests otherwise and after discussion with the sponsor's medical monitor.

For enzalutamide, if a patient experiences $a \ge Grade\ 3$ toxicity or an intolerable side effect (at the PI's discretion), withhold dosing for 1 week or until symptoms improve to $\le Grade\ 2$, then resume at the same or a reduced dose (120 mg or 80 mg). Please contact Sponsor's medical monitor for any questions.

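### For related Grade 3 thrombocytopenia, Protocol 5.4.6 lets PF-06952229 resume at platelets of 50,000/mm3 while the Table 3 Thrombocytopenia row holds it until 75,000/mm3, and nothing says which governs

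*Protocol*

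**What the plan says.** Four places in the protocol can be read as covering a patient held for related Grade 3 thrombocytopenia.

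- **5.4.6 Dose Delays.** Re-treatment after an interruption for related toxicity, or at the start of any new cycle, "may not occur until all of the following parameters have been met". The list is ANC ≥1,000/mm3, platelets ≥50,000/mm3, and recovery of non-hematologic toxicities. It continues: "If these conditions are met within 4 weeks of treatment interruption, PF-06952229 may be resumed". A pointer follows: "Refer to the Dose Reductions section for AEs that require dose reduction at the time of treatment resumption".
- **Table 3, Thrombocytopenia row, Grade 3.** "Hold PF-06952229 until platelets ≥75,000/mm3", with the instruction "Reduce PF-06952229 by 1 dose level".
- **Table 3, Hematologic row, Grade 3.** "Withhold dose until toxicity is Grade ≤2, or has returned to baseline within 2 weeks, then resume treatment at the same dose level". The row title carries no exclusion for thrombocytopenia.
- **5.4.7 text above Table 3.** "Hold PF-06952229 for related Grade 3 AEs with subsequent dose-reduction, if such AEs return to Grade <1 or baseline within two weeks".

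For Grade 4, the Thrombocytopenia row asks only that permanent discontinuation be considered, as does 5.4.5. The Hematologic row requires it, adding "Exclusion to this will require agreement between the investigator and sponsor".

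**The concern.** Two sites could treat the same platelet count differently and each point to protocol text in support. One would re-dose under 5.4.6; the other would keep holding under Table 3.

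The restart dose can differ too: one level lower under the Thrombocytopenia row, unchanged under the Hematologic row. That choice lasts. Under 5.4.7 a reduced dose carries into all later cycles, re-escalation within a patient is barred, and a patient needing more than two reductions comes off treatment unless investigator and sponsor agree otherwise.

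The setting gives some reason for care. The study had a partial clinical hold for bleeding, 5.4.8 suspends the trial if related bleeding exceeds 25%, and 5.7 prohibits anticoagulants and anti-platelet agents. An unclear platelet count for restarting sits badly with that caution.

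**Working it through.** The plan has no figure to reproduce here. The check is a comparison of the texts, followed by a count of events.

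**1. Is the 5.4.6 list only a floor, or also enough to resume?** The sentence containing "may not occur until all of the following parameters have been met" makes the criteria necessary. The sentence "If these conditions are met within 4 weeks of treatment interruption, PF-06952229 may be resumed" makes them sufficient. Without that second sentence, 50,000/mm3 would be a floor and would sit easily beneath a stricter rule elsewhere.

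**2. The competing instructions for one patient with related Grade 3 thrombocytopenia**

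| Source | Recovery needed | Restart dose |
|---|---|---|
| 5.4.6 | platelets ≥50,000/mm3, other criteria met | refers to 5.4.7 |
| Table 3, Thrombocytopenia | platelets ≥75,000/mm3 | one level lower |
| Table 3, Hematologic | Grade ≤2 or baseline | same level |
| 5.4.7 text | Grade <1 or baseline | reduced |

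**3. Size of the gap.** 75,000 − 50,000 = 25,000/mm3. From 50,000 to 74,999/mm3, with the other 5.4.6 criteria met, 5.4.6 permits dosing and the Thrombocytopenia row forbids it. At 75,000/mm3 or above both are satisfied.

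**4. Is precedence stated anywhere?**
- 5.3.2 sends dose adjustments to 5.4.4 and ranks nothing.
- 5.4.4 says that the worst of several toxicities decides. It does not rank competing rules for a single toxicity.
- 5.4.5 bases the need for a reduction at restart on the dose reduction criteria and gives no platelet count.
- The 5.4.6 pointer concerns which events need a reduced dose, not a different count. It does lead to the Thrombocytopenia row, because that row requires a reduction.
- The SAP is silent.

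**5. How often might it arise?** Appendix 10 (cut-off 19 June 2020, 20 patients enrolled) lists Grade 3 events as 3 related + 21 unrelated + 1 with relationship not reported = 25. The unrelated events as itemised are 3 + 2 + 2 + 2 + 2 + 10 = 21. Adding 2 Grade 4 events gives 25 + 2 = 27, of which 0 are thrombocytopenia.

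**6. Does either count enter a statistical quantity?** The thrombocytopenia DLT definition in 3.2 rests on grade, duration, bleeding and transfusion, and uses neither count. The DLT criterion for a dose delay longer than 2 weeks sits under the heading for nonhematologic and non-hepatic events. No sample size or analysis uses either count.

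**The case against.** The strongest reply is that this is a general floor plus a specific rule. Table 3 pairs named rows with general ones: bilirubin beside Non-hematologic, and Thrombocytopenia and acute hemoglobin reductions beside Hematologic. A physician with a thrombocytopenia case has a row of that name. The 5.4.6 pointer leads there, 5.4.5 says that restart dose follows the reduction criteria, and waiting for 75,000/mm3 satisfies 5.4.6 as well. On that view all that is missing is a cross-reference.

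Much of this stands. The specific, stricter row is the natural reading and probably the intended one. But it has to be inferred against a sentence in 5.4.6 that grants permission to resume, and against a Hematologic row whose title does not exclude thrombocytopenia.

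Three stronger readings are tempting and are not supported.

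- A reader might count four distinct recovery standards. Two are platelet counts and two are CTCAE grades, and the documents do not give the platelet cut-offs for Grades 1 and 2, so the grade-based standards cannot be shown to differ from the counts. The <1 in 5.4.7 may also be a misprint or a lost sign, since the same section uses ≤1 elsewhere.
- A reader might infer that Grade 4 patients can resume only with sponsor agreement. That comes from the Hematologic row; the Thrombocytopenia row and 5.4.5 only ask that discontinuation be considered.
- A reader might connect the point to the earlier hemorrhages. The documents do not link those events to low platelets.

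**Conclusion.** The inconsistency is real and of low severity. For related Grade 3 thrombocytopenia, 5.4.6 as written allows re-dosing at 50,000-74,999/mm3, where the Thrombocytopenia row requires a hold. The two Table 3 rows that could be applied also give different restart doses. The protocol does not say which text governs.

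This assumes that the other 5.4.6 criteria are met and that a site acts on the words of the section it consults. A site that goes straight to the named row would do what was probably intended.

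The case is likely to be uncommon, given no thrombocytopenia among the 27 Grade 3-4 events in 20 patients. The documents do not allow an estimate of how many later patients would meet it. The point is a precautionary safety clarification: no endpoint definition, sample size or stated figure changes.

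**What to change.** Three short edits in the next amendment:

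1. In 5.4.6, change the platelet item to: *≥50,000/mm3 (≥75,000/mm3 after an interruption for related Grade 3 or higher thrombocytopenia, per Table 3)*.
2. Retitle the Table 3 general row *Hematologic (other than thrombocytopenia)*. Done alone, this would remove that row's Grade 4 discontinuation rule, and the agreement needed for an exception, from thrombocytopenia. If the sponsor wants to keep them, copy both into the Grade 4 cell of the Thrombocytopenia row.
3. In 5.4.7, state that where Table 3 gives a toxicity-specific recovery criterion, it governs over the general text.

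No visits, procedures or analyses are added. The downside is a slightly longer hold for a few patients whose counts recover to between 50,000 and 74,999/mm3.
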